3.1.4 PK sampling

One blood sample for PK analysis will be taken prior to the morning dose at Week 1 (Visit 4), Week 4 (Visit 7) and Month 3 (Visit 9). During Month 4 (Visit 10), blood samples for PK analysis will be taken before the morning dose and up to 5 hours post-dose. Patients entering the extension will take one blood sample for PK analysis prior to the morning dose at visit 13.

3.1.5 OGTT

In order to study effects of AZD1656 on post-prandial glucose control, an OGTT, with collection of blood samples over 2 hours, will be performed at baseline (Week 0, Visit 3, no IP at this visit) and 4 months (Visit 10). This test will only be performed in a subgroup of the study population (approximately half the patients in the study) at selected sites. For details regarding the OGTT, see section [6.3.1.4](#).

3.1.6 Hyperglycaemia during study

After randomization, definitions of hyperglycaemia and the use of rescue medication will apply, see Section [5.6.1](#). Patients will receive written instructions on the need for plasma glucose assessments in case of hyperglycaemia symptoms, and to contact the investigator if two consecutive fasting morning plasma glucose values are >11 mmol/L (198 mg/dL). The investigator must also at every study visit consider extra plasma glucose monitoring, especially if the patient's glucose levels start to deteriorate. Patients meeting criteria for hyperglycaemia should receive treatment with basal night-time insulin in addition to metformin and the randomized IP treatment.

3.1.7 Hypoglycaemia

Patients will receive instructions regarding hypoglycaemia symptoms and treatment, and to contact the clinic if plasma glucose is <3 mmol/L. Patients experiencing hypoglycaemia during the titration period (until Visit 7) may have their dose of AZD1656/placebo/glipizide reduced as judged by the investigator (open dose reduction in the open-label AZD1656 arm and simulated dose reduction in the AZD1656 fixed-dose arms and placebo arm). The reduction in dose can be done if the patient experience two or more hypoglycaemic events with documented plasma glucose below 3.0 mmol/L (54mg/dL) within a week or if the investigator judged that there is a safety concern for the patient to stay on the same dose as before. Such a dose reduction can only be done once, if safety concerns remain despite a dose reduction, the patient must be discontinued.

[figure not shown]
The investigator must continuously evaluate if study participation is safe for the individual patient and if recurrent hypoglycaemia despite dose reduction, if applicable, patient may have to be discontinued from study (for study specific discontinuation criteria see Section [5.8](#)).

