3.1.3 Treatment with AZD1656/placebo/glipizide and titration overview

The investigational products (IPs) in this study for patients in cohort 1 are the blinded, randomized treatments of AZD1656/placebo, glipizide/placebo and placebo/placebo. Patients in cohort 2 will be assigned the open treatment of AZD1656.

For patients in cohort 1, the dose of glipizide and of AZD1656 in the titrated arms will be increased stepwise on a weekly basis in a blinded fashion during the first 4 weeks after randomization. On Visits 4, 5 and 6 the dose of blinded treatment will be increased if the fasting morning plasma glucose analysed at the clinic at the specific visit is >6.1 mmol/L (110mg/dL), and no conditions (eg hypoglycaemic risk) oppose a dose increase according to investigator's judgement, See [Figure 2](#). For patients in cohort 2, the open-label dose of AZD1656 will be increased in the same way, but the increase will be open to both the investigator and the patients. See [Table 1](#) for dose steps during the titration period. Once the dose of AZD1656/glipizide/placebo is established, patients will continue on the dose achieved for the rest of the study, unless reduction is needed due to hypoglycaemia, as judged by the investigator (dose reductions will be simulated in the fixed AZD1656 arm and the placebo arm).

There will be a simulated dose increase in the placebo arm and the fixed dose arms with AZD1656.

Figure 2 Dosing overview during titration

[figure not shown]

Table 1 Schematic overview of possible daily doses of AZD1656 and glipizide during the initial titration period

	Visit 3	Visit 4	Visit 5	Visit 6
	0 = baseline	After 1 week	After 2 weeks	After 3 weeks
AZD1656 open label dose span	20mg (10mg bid)	50mg (25mg bid)	100mg (50mg bid)	200mg (100mg bid)
Randomized treatment				
AZD1656 arm higher dose span	20mg (10mg bid)	50mg (25mg bid)	100mg (50mg bid)	200mg (100mg bid)
AZD1656 arm lower dose span	10mg (5mg bid)	20mg (10mg bid)	50mg (25mg bid)	140mg (70mg bid)
AZD1656 fixed dose arm	40mg (20mg bid)	40mg (20mg bid)	40mg (20mg bid)	40mg (20mg bid)
AZD1656 fixed dose arm	20mg (10mg bid)	20mg (10mg bid)	20mg (10mg bid)	20mg (10mg bid)
Glipizide arm	5mg (5 + 0mg)	10mg (5mg bid)	15mg (10 + 5mg)	20mg (10mg bid)
Placebo arm	Placebo	Placebo	Placebo	Placebo

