5.5.2 Doses and treatment regimens

Treatment during run-in

During the run-in period (Weeks –2 [Visit 2] to Week 0 [Visit 3]) each patient will switch to study metformin and they will receive a box containing 100 tablets of 500mg and/or a box containing 56 tablets 850mg study metformin depending on individual dose metformin. Patients' initial dose of metformin will remain unchanged.

Randomized treatment period

The randomized treatment period starts at Week 0 (Visit 3) with a titration period of 4 weeks, where the patients will receive 1 double-blind kit containing either of AZD1656 starting dose of 10mg, 20mg, 20mg (fixed dose), 40mg (fixed dose), placebo, glipizide 5mg or 20mg open AZD1656. The patients will be titrated stepwise in a blind fashion to the target dose and the dose will be increased, if appropriate, weekly as they visit the clinic. Each week they will receive a new set of AZD1656 and glipizide with a higher strength. For patients in the fixed dose AZD1656 and placebo arms, the titration will be simulated and no increase in dose will take place. If a dose increase is not considered appropriate by the investigator, they will instead receive another set of IP that corresponds to the previous tolerated dose.

Randomized treatment period

After 4 weeks of titration, each patient will continue on the highest dose achieved up to 4 months as well as during the optional 2-month extension. The patients will receive a new kit of IP once a month, ie, Visit 8 and Visit 9. Patients entering the extension period will receive a new kit of IP once a month, ie, visit 10 and extension visit 12.

One kit of IP consists of:

- A wallet consisting of 1 blister of AZD1656, dose 10mg, 20mg, 40mg, 50mg, 100mg, 140mg, 200mg or placebo and a wallet consisting of a blister of glipizide 5mg, 10mg, 15mg or 20mg or placebo. Each blister card of AZD1656 will have 10 rows, where 1 row is 2 doses consisting of 2 tablets each. The glipizide blisters will also consist of 10 rows where 1 row is 2 doses consisting of 2 capsules each.

Study medication should be returned by the patients for drug accountability.

Treatment during the extension period:

The patients in the extension will continue on the same blinded (cohort 1) or open treatment (cohort 2) as during the 4 months study.

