5.8 Discontinuation of investigational products

Patients may be discontinued from IP in the following situations:

1. Patient decision. The patient is at any time free to discontinue treatment, without prejudice to further treatment.
2. AE.

3. Severe non-compliance to study protocol as judged by the investigator and/or AZ/ICON Clinical Research.
4. Risk to patients as judged by the investigator and/or AZ
5. Patient lost to follow-up.
6. Incorrectly randomized patient, see Section 3.1.

Development of any study specific criteria will lead to discontinuation from IP:

- Patient uses amiodarone, warfarin, rimfampicin or potent CYP450 inhibitors, such as, but not limited to, ketokonazole and macrolide antibiotics during the study should be discontinued from the study.
- Patients who despite dose reduction of IP once, experiences more than one major hypoglycaemic event with need for external assistance due to impaired consciousness, or with other hypoglycaemic event(s) resulting in safety concerns with continued IP treatment, should be discontinued from the study. The hypoglycaemic event should be recorded in the appropriate CRF modules.
- Patients with remaining hyperglycemia despite maximum tolerable dose of basal night-time insulin, according to the investigator, should be discontinued from the study and receive appropriate glucose corrective treatment. For the definition of hyperglycemia at different time points during study, see section 5.6.1
- Patient who develops a condition contraindicating treatment with metformin or glipizide during the study should be discontinued. Conditions include, but are not limited to, renal impairment with GFR <60 ml/min, shock and diabetic ketoacidosis. However, temporary discontinuation of metformin and/or IP (up to 7 days) due to e.g. acute illness or radiological investigations with iodinated contrast media is allowed
- Increase in plasma CK levels to more than 10 x ULN on two consecutive measurements that cannot be ascribed to a benign condition or situation.
- Increase in AST and or ALT to more than 5 x ULN
- ALT or AST more than 3 x ULN and total bilirubin more than 1.5 x ULN.

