5.8.1 Procedures for discontinuation of a patient from investigational product

All discontinuation due to hypoglycaemia should be according to the judgement of the investigator, ie, the investigator should be able to allow the patient to continue (even after a major hypoglycaemic event) if there are clear circumstances explaining the event, and the risk for a recurrence is low.

If the patient is discontinued from IP, the patient is also discontinued from the study. As far as possible they will be seen and assessed by the investigator at an end of study visit and then at a follow-up visit scheduled according to the study protocol and including the procedures described in Section 5.8.1. If the patient does not agree to this option, a modified follow up (eg, telephone contacts) should be arranged, if agreed to by the patient and in compliance with local data privacy laws/practices. The approach taken should be registered in the eCRF. Follow-up is not applicable if the patient is lost to follow-up.

For patients discontinuing due to liver enzyme criteria, special evaluation will be performed, see [Appendix E](#).

If a patient is to be withdrawn from the study, see Section 5.9.

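### The protocol contradicts itself on whether the dose may be reduced for hypoglycaemia after Visit 7, and on whether the hypoglycaemia stopping rule binds the investigator

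*Protocol*

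**What the plan says.** **Dose reduction.**
- Section 3.1.3, on dosing after titration: "patients will continue on the dose achieved for the rest of the study, unless reduction is needed due to hypoglycaemia, as judged by the investigator". No end date is given.
- Section 3.1.7: "Patients experiencing hypoglycaemia during the titration period (until Visit 7) may have their dose" reduced at the investigator's judgement. The section adds that this can be done only once.
- Section 5.5.2: after the four titration weeks, "each patient will continue on the highest dose achieved up to 4 months", and likewise in the extension. No exception for hypoglycaemia is mentioned.

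**Stopping.**
- Section 3.1.7: "if safety concerns remain despite a dose reduction, the patient must be discontinued".
- Section 5.8: study-specific criteria are introduced as leading to discontinuation of study drug. The hypoglycaemia criterion covers a patient who, despite one dose reduction, "experiences more than one major hypoglycaemic event with need for external assistance due to impaired consciousness", or who has other hypoglycaemic events that raise safety concerns.
- Section 5.8.1: all discontinuation for hypoglycaemia is to follow the investigator's judgement, and "the investigator should be able to allow the patient to continue (even after a major hypoglycaemic event") when the event has a clear explanation and recurrence is unlikely.

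**Consequence.** Section 5.8.1 also states that a patient taken off study drug leaves the study. Section 12.2.6.1 makes LOCF on the full analysis set the primary analysis of HbA1c.

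**The concern.** Hypoglycaemia is the harm that the protocol singles out for special attention in 1.4.3, and these sections tell a site what to do when it occurs. If they disagree, two investigators who each follow the protocol can treat the same patient differently: one reduces the dose and the other does not, or one stops treatment and the other continues. The synopsis plans about 130 centres for 450 randomized patients, or 450/130 ≈ 3.5 per centre, so each site will meet the problem rarely and interpret it largely alone.

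There is also a consequence for the estimate. Because stopping drug ends participation, the reading a site adopts can determine whether a patient contributes an observed month-4 HbA1c or an earlier value carried forward.

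**Working it through.** No figure in the protocol depends on these rules, so the check is to set the sections side by side and then ask what can be quantified.

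**1. Is a reduction available after Visit 7?**
- 3.1.3: yes, for the rest of the study.
- 3.1.7: described for titration only; no later step is given.
- 5.5.2: the highest dose achieved is kept. Read literally, this does not accommodate even a reduction made before Visit 7, since that patient is no longer on the highest dose achieved.

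The three sections do not give a site one answer.

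**2. How long does the ambiguity last?** Table 2 puts Visit 7 at day 28, Visit 10 at day 120 and Visit 13 at day 180.
- Main study: 120 − 28 = 92 days; 92/120 = 77%.
- With the extension: 180 − 28 = 152 days; 152/180 = 84%.

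These are fractions of the calendar. They say nothing about how many patients or events are affected.

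**3. Does the first conflict reach the stopping rule?** Take a patient whose first major events occur after Visit 7. The 5.8 criterion is conditional on one earlier reduction. Under 3.1.3 a reduction can be made, and the criterion can then be met. Under 3.1.7 no reduction is described at that stage, so whether the criterion can be met is unclear.

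**4. Is the stopping rule binding?** Take a patient who has been reduced once and then has more than one major event, each with a plausible explanation.
- 5.8: the criterion is met and discontinuation follows.
- 3.1.7: if a safety concern remains, discontinuation is compulsory.
- 5.8.1: the decision is the investigator's.

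Section 5.3 does not settle precedence. It says that discontinuation after randomization is governed by study-specific criteria or by investigator judgement, without ranking them.

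**5. What happens to the primary endpoint?** A stopped patient leaves the study. Table 2 schedules HbA1c at Visits 7, 8, 9 and 10, so a patient stopped between Visit 7 and Visit 10 will normally have a post-baseline value to carry forward and stay in the full analysis set. What is lost is the observed month-4 value, not necessarily the patient.

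**6. Can the effect be sized?** No. No hypoglycaemia stopping rate is given, and the 4 to 5% drop-out allowance in 12.3 is not attributed to any cause. For scale only, suppose that a fraction d of an arm has a carried-forward value in place of the month-4 value and that the two differ on average by g HbA1c points. The arm mean then moves by d × g. With assumed d from 0.05 to 0.15 and g from 0.2 to 0.6, the shift runs from 0.05 × 0.2 = 0.01 to 0.15 × 0.6 = 0.09, against the design difference of 0.7. This is a shift in one arm's mean. The treatment difference moves only if d or g differs between arms, which the wording conflict does not in itself produce.

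**The case against.** The strongest reply is that most of the text can be read together. Section 3.1.7 never says that reduction is allowed *only* until Visit 7, and 5.5.2 may be a dosing and supply summary that is merely silent on the exception. A safety concern is itself a judgement, so 5.8.1 can be taken as saying who makes it. The permission in 5.8.1 speaks of a single major event, whereas 5.8 requires more than one after a reduction. Much of this is fair, and it narrows the point. It does not remove it. A site reading 3.1.7 finds a stated end to the reduction window that 3.1.3 lacks. The opening statement in 5.8.1 covers every hypoglycaemia discontinuation, which cannot stand beside a counted trigger in 5.8 that leads to discontinuation.

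Four stronger readings might be inferred, and the protocol does not support them:
- *Section 3.1.7 contradicts itself.* Its second statement, that "if recurrent hypoglycaemia despite dose reduction, if applicable, patient may have to be discontinued from study", has a different trigger. Recurrence may or may not leave a safety concern; where it does, the compulsory rule applies. Both can hold.
- *Simulated reductions in the fixed-dose and placebo arms make the rule differ by arm.* The simulation protects the blind, and blinded investigators apply 5.8 identically in every cohort 1 arm.
- *Month-4 data loss will depend on arm because of this conflict.* Any arm difference would come from how often each treatment causes hypoglycaemia, and would exist under a fully reconciled rule.
- *A patient with late events cannot be stopped.* Section 5.8 separately allows discontinuation for an adverse event or for risk as judged by the investigator.

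The early clinical data also suggest low frequency. Section 1.4.2 reports four events below 3 mmol/L, none with impaired consciousness or need for assistance, though the studies lasted four weeks at most.

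**Conclusion.** The point holds in two specific places. First, 3.1.3, 3.1.7 and 5.5.2 disagree on dose reduction after Visit 7, which leaves the reach of the 5.8 hypoglycaemia criterion unclear for events that first arise then. Second, 3.1.7 and 5.8 make stopping compulsory once their conditions are met, while 5.8.1 leaves it to the investigator. Sites may therefore handle the same patient differently.

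The effect on the primary analysis is possible but cannot be sized from the protocol. It depends on an unstated stopping rate and on how far carried-forward values differ from month-4 values. LOCF and the end-of-study visit sought under 5.8.1 limit the loss of patients from the analysis. No stated figure becomes wrong. The case for correction rests mainly on contradictory instructions for a principal safety rule.

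**What to change.** Amend the protocol in two places.
1. Reconcile 3.1.3, 3.1.7 and 5.5.2 so that they give one answer on whether a reduction for hypoglycaemia is available after Visit 7 and during the extension.
2. Reconcile 3.1.7, 5.8 and 5.8.1 into one hypoglycaemia discontinuation criterion, stated once and cross-referenced elsewhere. It should say whether investigator judgement can override it, and whether it can be met without a prior dose reduction.

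Which clinical rule to adopt is for the sponsor to decide; the statistical requirement is only that it be single and unambiguous. The cost is amendment wording and a communication to sites, with no new visits, samples or procedures.

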3.1.8 Adjudication of cardiovascular events

An Adjudication Committee will be appointed to evaluate all deaths and suspected cardiovascular events from the time point of randomization until study completion and perform an event categorisation. The adjudication procedure will be defined in a specific adjudication charter and will include events of death, myocardial infarction/acute coronary

syndrome, stroke, events of cardiac heart failure and arrhythmia. This evaluation will be performed on blinded data.

Figure 3 Study flow chart

Glip. = Glipizide.

Table 2 Study Plan

Activity	Enrolment period	Run-in period	Randomized treatment period								Extension		Follow-up period
			1	2	3	4	5	6	7	8	9	10	
Visit number	1	2	3	4	5	6	7	8	9	10	12	13	11 or 14 ^o
Study week / month	W -4	W -2	W0	W1	W2	W3	W4	M2	M3	M4	M5	M6	2 weeks ± 5 days after last visit
Study day and visit window	-28 to -18	-16 to -12	0	7(±2)	14(±2)	21(±2)	28(±2)	60(±5)	90(±5)	120(±5)	150 (±5)	180(±5)	
Informed Consent	x					(x ⁿ)	(x ⁿ)	(x ⁿ)	(x ⁿ)	x ⁿ			
Genetic informed consent ^b	(x)	(x)	(x)										
Randomization			x										
Inclusion/exclusion criteria	x	x	x										
Demography and nicotine/alcohol use	x									x ^c			
Medical/surgical history	x												
Physical examination	x		x				x	x	x	x		x	x
12-lead digital ECG	x		x	x			x	x	x	x	x	x	x
Height	x												
Vital signs (pulse, BP)	x		x	x	x	x	x	x	x	x	x	x	x
Weight	x		x				x		x	x		x	x
Waist and hip circumference			x							x		x	
Test for HIV, Hepatitis B and C	x												
Drug screening test	x												
FSH, LH ^a	x												
Safety blood and urine sampling	x		x	x ^d	x ^d	x ^d	x	x	x	x	x	x	x
Fasting plasma glucose (FPG) ^e	x		x	x	x	x	x	x	x	x	x	x	x
HbA1c	x		x				x	x	x	x	x	x	
Efficacy blood samples (Insulin, C-peptide, lipids and CRP)	x ^f		x				x			x	x	x	
SMPG ^g		x	x	x	x	x	x	x	x	x	x	x	
Distribution and review of Patient Diary		d	d/r	d/r	d/r	d/r	d/r	d/r	d/r	d/r	d/r	r	
PK blood sampling for AZD1656				x ^h			x ^h		x ^h	x ⁱ		x ^h	
Diet and lifestyle advice		x	x	x	x	x	x	x	x	x	x	x	x

Activity	Enrolment period	Run-in period	Randomized treatment period								Extension		Follow-up period
			1	2	3	4	5	6	7	8	9	10	
Visit number	1	2	3	4	5	6	7	8	9	10	12	13	11 or 14 ^o
Study week / month	W-4	W-2	W0	W1	W2	W3	W4	M2	M3	M4	M5	M6	2 weeks ± 5 days after last visit
Study day and visit window	-28 to -18	-16 to -12	0	7(±2)	14(±2)	21(±2)	28(±2)	60(±5)	90(±5)	120(±5)	150 (±5)	180(±5)	
Contact IVRS/IWRS	x	x	x	x	x	x	x	x	x	x	x		
Dispense of blinded IP (AZD1656, placebo, or glipizide)			x	x	x	x	x	x	x	x	x		
Dispense of open metformin ^m		x		x	x	x	x	x	x	x	x		
Dispense of open AZD1656			x	x	x	x	x	x	x	x	x		
Drug accountability, IP (AZD1656, placebo or glipizide)				x	x	x	x	x	x	x	x	x	
Drug accountability, metformin ^m			x	x	x	x	x	x	x	x	x	x	
Concomitant medication	x	x	x	x	x	x	x	x	x	x	x	x	x
Genetic blood sampling ^b			(x)	(x)	(x)	(x)	(x)	(x)	(x)	(x)	(x)	(x)	(x)
AE / SAE collection ^k	x	x	x	x	x	x	x	x	x	x	x	x	x
OGTT ^l			x							x			

d: distribution, r: review, d/r: distribution and review

a For females where postmenopausal status needs to be confirmed, see Section 4.1

b After the patient has signed the genetic informed consent at any of visits 1, 2 or 3, the blood sample can be taken at any visit after randomization.

c Nicotine use only.

d Excluding p-lactate and cystatin-C.

e FPG to be analysed immediately locally at the clinic. A venous sample will also be sent to the central laboratory.

f No lipid status or CRP at enrolment visit.

g Self-monitoring of Plasma Glucose at home. Section 3.1.2 and Section 6.3.1.3.

h One blood sample for PK analysis before morning dose (trough sample).

i PK samples will be taken before morning dose and up to 5 hours post-dose. See Section Section 6.6.

k All AEs will be collected from the time of the first administration of IP until the end of the study (including follow-up visit). Before the first administration of IP, only SAEs will be collected.

l OGTT will be performed in a subgroup of patients at selected sites. Blood sampling before and during 2 hours after glucose intake. See Section 6.3.1.4.

m Depending on the individual dose, and hence the individual consumption of different tablet strengths, metformin dispensing and drug accountability occasions may differ between patients.

n The informed consent form for the optional extension period should be signed at any visit but no later than at visit 10.

o For patients completing the study at 4 months, the follow-up visit no 11 will be used. For patients consenting to the extension, the follow-up visit no 14 will be used

